This study provides critical additions to previous work by: 1) conducting a novel investigation of arterial stiffness and endothelial dysfunction as possible mechanisms accounting for the observed effects of GnRHa on cognition; 2) studying younger women to better distinguish the effects of E2 deficiency from those of aging; 3) incorporating a true E2 add-back condition to distinguish between E2 and progesterone effects and 4) extending the duration of GnRHa treatment to help clarify cognitive effects.

**Specific Aim 1.** Determine the effects of 6 mo of ovarian hormone suppression with GnRHa on:

- 1) Patterns of activation in the PFC during tasks of executive cognitive function using functional magnetic resonance imaging (fMRI).
- 2) Arterial stiffness determined by ultrasound measures of carotid artery compliance and pulse wave velocity, and endothelial function measured by brachial artery flow-mediated dilation (FMD).

**Hypothesis 1a.** GnRHa treatment will significantly decrease PFC activation, increase arterial stiffness and decrease endothelial function compared to placebo.

**Hypothesis 1b.** Changes in PFC activation with GnRHa will be inversely associated with expected increases in arterial stiffness and positively associated with expected declines in endothelial function.

**Specific Aim 2.** Determine the effects of 3 mo of exogenous E2 add-back on:

- 1) Patterns of brain activation in the PFC during tasks of executive cognitive function using fMRI.
- 2) Arterial stiffness and endothelial function as measured in Specific Aim 1 (2).

**Hypothesis 2a.** E2 add-back will restore PFC activation, arterial stiffness and endothelial function to baseline (pre-GnRHa) levels.

**Sub-study Exploratory Aim:** A sub-study will enroll late-perimenopausal and postmenopausal women who have recently completed vascular testing under another protocol. The protocol for participants in this Sub-study is limited to cognitive testing and fMRI scanning at a single timepoint. The aim of this Sub-study is to compare vascular and cognitive measures in the above intervention population (premenopausal women before and after placebo or GnRHag with or without exercise) with late-perimenopausal and postmenopausal women. These comparisons will generate preliminary data for an anticipated R01-level application.

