**2. Innovation.** This study proposes an innovative interventional paradigm to study vascular mechanisms underlying the effects of  $E_2$  on cognitive function. In addition to providing new mechanistic insights, this study addresses several shortcomings of previous work that used fMRI to assess changes in brain activation with ovarian hormone suppression. First, we will be better able to determine the effects of  $E_2$  deficiency from those of aging by examining the effects of GnRHa in younger women. Second, we will have a true  $E_2$  add-back condition to isolate the effects of  $E_2$  as opposed to other ovarian hormones or effects of GnRHa itself on cognition. Third, women will be studied after 6 months of ovarian hormone suppression. This longer duration is likely to produce even more pronounced/consistent effects on brain activation. The use of fMRI in this study is resource-intensive. However, fMRI is widely available, requires no ionizing radiation, and is sensitive to early brain changes occurring prior to clinically obvious cognitive impairment. This approach is thus consistent with identifying subtle early changes in cognitive function that would precede clinical symptoms and functional impairment when interventions are most likely to be effective. Further, this study design allows us to glean information from shorter-term studies, rather than studying women over years of  $E_2$  deficiency. This project would not be possible solely within the K23 funding mechanism without [name] collaboration. Enrolling participants from [name] FAME study investigating the bioenergetic and metabolic consequences of the loss of ovarian function in women saves on recruitment and screening costs, as well as the substantial cost of GnRHa treatment. This permits funds from this K23 award to support the fMRI imaging and analysis.

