Separate from the parent FAME study, women randomized to GnRHa and no exercise will complete an additional 3 months of GnRHa + transdermal E2 add-back, with vascular and cognitive/fMRI testing at 9 months (Fig 2).

**Sub-study.** An additional group of up to 30 late-perimenopausal or postmenopausal women who have had carotid artery compliance and brachial artery FMD performed within the last 6 months will also be enrolled. There is no intervention performed in this group, rather, they will serve as a comparison to the other premenopausal intervention groups. Similar to premenopausal women, late perimenopausal and postmenopausal women will be excluded for: Mini Mental State Examination score  $\leq 27$ , history of neurologic disease or major psychiatric illness, major depressive episode within the past 12 months, history of learning disability, < high-school education, or contraindications to MRI. Experimental procedures in this group of participants will be limited to cognitive testing, fMRI and apolipoprotein ε4 genotyping.

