suppression of pituitary gonadotropins and ovarian hormone secretion; repeated monthly dosing maintains suppression of ovarian function. Leuprolide has been used clinically for up to 1 yr without serious adverse events, although there may be a decrease in bone mineral density that recovers slowly following cessation of treatment. Side effects are those typical of E2 deficiency including hot flashes, headaches, nausea, emotional lability, decreased libido, acne, myalgias, sleep disorder, reduction in breast size, and vaginal dryness. There may be a development or worsening of depression and the occurrence of memory disorders. In studies of women with uterine fibroids, GnRHa 3.75 mg/mo induced amenorrhea in 61%, 86%, and 90% of women after 1, 2, and 3 mo of treatment, respectively. Return of menses typically occurred within 2-3 mo of cessation of therapy. Injections will be administered in a blinded manner, but participants on GnRHa may know their assignment because of the induction of amenorrhea and menopausal symptoms. Subjects will be instructed not to discuss their assignment with the outcome assessors. Subjects receiving an additional 3 mos of GnRHa in this sub-study will also receive weekly transdermal 17 $\beta$ -E2 add-back therapy (0.075 mg/d) and 1 cycle of MPA (5mg/d x 12 d at week 6 of E2 add-back). The rationale for the MPA is to prevent break-through bleeding, and thus enhance participant retention, and to prevent potential endometrial hyperplasia, although this is unlikely to occur during the 3-mo intervention. Additionally, we are interested in isolating the effects of E2 alone and not in combination with MPA because of the potential antagonizing effects of MPA on E2 action and because MPA has been shown to have negative effects on cognition. Thus, although technically a combination HT intervention, the add-back is E2-based, with minimal progesterone exposure. The first 6 months of drug intervention will be done as part of the FAME study, thus there will be no cost to this proposed sub-study during this period. Study drug for the 3-month E2 add-back portion unique to this sub-study will be paid for by the sub-study (Figure 3).

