This model of ovarian hormone suppression does not mimic the gradual process of natural menopause. However, menopause occurs at a time when women are also beginning to experience other age-related physiological changes, making it difficult to isolate the effects of aging from those of ovarian failure. Because this is a mechanistic study, this model strengthens the design to allow us to effectively study how changes in arterial stiffness and endothelial function due to loss of ovarian function may mediate changes in cognition. Ideally we would have a placebo group during the add-back portion of the study; due to resource constraints and subject burden this was not included. To preserve blinding, cognitive testing and fMRI analysis will be performed by personnel blinded to subject group. Ideally we would measure changes in cerebral arterial compliance in response to ovarian hormone suppression, but these methods have not been developed. The measures of peripheral vascular function proposed for this study are non-invasive, well- validated, and have been correlated with white matter changes in the brain.

Participant burden, location and scheduling of equipment preclude performing the vascular and fMRI testing on the same day. Although this raises the possibility of day-to-day variability affecting our results, this will be minimized by testing all participants during the early follicular phase (i.e., days 2-6) of the menstrual cycle at baseline. Testing for visits 2 and 3 (for subset receiving add-back) will be done while participants are receiving GnRHa. We will measure E2 concentrations at each visit to allow us to adjust for differences in hormone levels and tests will be scheduled at the same time of day. Data have shown moderate to strong reliability of fMRI BOLD signal changes and cardiovascular reactivity when tested simultaneously on two occasions 3 months apart.

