### **3.g. Interpretation and future directions**

**Specific Aim 1** will determine the effects of ovarian hormone suppression on PFC activation, arterial stiffness and endothelial function. Previously published and preliminary data suggest we will observe the hypothesized negative effects on brain activation and vascular function in response to GnRHa treatment. If changes in PFC activation and vascular function are correlated as we hypothesize, this would lead us to investigate whether other therapeutic or lifestyle interventions that target vascular function (i.e. exercise) could counteract the negative effects of ovarian suppression. Future studies could also measure intra-cranial blood flow and compliance, structural brain changes or brain expression of E2 receptors to more closely examine effects on the brain. If changes in PFC activation are not correlated with changes in vascular function, this would lead us to investigate other possible mechanisms for the negative effects of ovarian hormone suppression on cognition (e.g. inflammation, oxidative stress, amyloid accumulation, tau hyperphosphorylation).

**Specific Aim 2** will isolate the effects of E2 on PFC activation, arterial stiffness and endothelial function. If E2 add-back restores PFC activation and vascular function as hypothesized, this would support a role for E2 and further investigations into mechanisms and interventions to counteract the effects of E2 deficiency. If PFC activation and vascular function are not restored, or only partially restored, this would lead us to investigate the contributions of other ovarian hormones or effects of GnRHa.

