#### **c. Potential Risks.**

- Vascular measures (brachial artery FMD, carotid artery compliance and pulse wave velocity). There are no known risks to participants associated with these procedures. Some participants may have discomfort in the hand (pins and needles) during the cuff occlusion portion of the FMD measurement.
- Functional magnetic resonance imaging (fMRI) measurements. The magnetic field of the MR environment has the potential to cause burns or bodily injury if ferrous metal objects are implanted in the body, or if personal articles containing ferrous material are brought into the environment. The risk of MRI to pregnant women and fetuses is currently unknown. The MRI may cause discomfort due to scanner noise. There may be some discomfort from lying still and in one position for a long time. At sufficient exposure levels, peripheral nerve stimulation is perceptible as "tingling" or "tapping" sensations. PNS symptoms will usually subside shortly after the scan is completed. Participants may feel nervousness or feelings of claustrophobia. There is a risk that the image will reveal an observation concerning an individual research participant that has potential clinical importance but is beyond the aims of this protocol. In the event of the confirmation of a significant anomaly in a participant's brain image, this information will likely be distressing to the participant.
- Cognitive testing. Subjects may experience frustration or anxiety during the testing session. It is possible that this testing could reveal previously unrecognized significant cognitive impairment that could be distressing to the subject.
- Study drugs. As participants in the FAME study, all participants in this proposed research will be randomized to receive placebo (saline) or GnRHa (leuprolide acetate) 3.75 mg/mo by intramuscular injection every month for 6 months (6 doses), plus or minus exercise. Women randomized to GnRHa and no exercise will receive 3 additional monthly doses after completion of the FAME study, for a total of 9 doses. During these 3 additional months, these women will also receive weekly transdermal 17 $\beta$ -estradiol 0.075 mg/d (12 doses), and oral medroxyprogesterone acetate 5mg/day for 12 days (12 doses) at the beginning of week 6 of estradiol therapy to minimize breakthrough bleeding and thereby enhance

participant retention.

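### Aim 2 is said to isolate estradiol, but the add-back phase has no control and adds MPA, so it can show only a within-woman change under estradiol-based add-back

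*Combined protocol and SAP*

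**What the plan says.** Four places claim separation of effects:

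- 3.g, Specific Aim 2: the aim "will isolate the effects of" estradiol on prefrontal activation, arterial stiffness and endothelial function.
- Specific Aims: the study has a true estradiol "add-back condition to distinguish between" estradiol and progesterone effects.
- 1.b, Estrogen and cognitive function: the add-back group is offered as a way to set estradiol apart from other ovarian hormones and from direct GnRHa effects.
- 2, Innovation: estradiol is to be isolated "as opposed to other ovarian hormones or effects of GnRHa itself on cognition".

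The design is described elsewhere:

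- 3.b, Methods: "women randomized to GnRHa and no exercise will complete an additional 3 months of GnRHa" together with transdermal estradiol, with testing at 9 months.
- Protection of Human Subjects, Potential Risks: these women also receive "oral medroxyprogesterone acetate 5mg/day for 12 days (12 doses) at the beginning of week 6 of estradiol therapy".
- 3.b, Drug intervention: the regimen is acknowledged as E2-based "although technically a combination HT intervention". Exposure to MPA is kept small partly "because MPA has been shown to have negative effects on cognition".
- 3.f, Limitations: "Ideally we would have a placebo group during the add-back portion of the study". Resources and subject burden are given as the reasons for leaving it out.
- 3.c: the vascular effect of add-back is tested with a paired t test on 17 women. Drug intervention puts the number continuing at 10.

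**The concern.** A single-arm before-and-after contrast estimates the total change over the period, whatever caused it. Here that total contains estradiol, one MPA course, three more months of GnRHa, three more months of elapsed time and a third test session. No comparison in the plan removes any of these. To isolate estradiol would require a contrast in which the other components are the same and estradiol differs.

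What is at stake is what Aim 2 may conclude. Isolation of estradiol is presented as a main advance over earlier work, so readers will take a positive 9-month result as answering that question. The converse inference is also insecure. If function is not restored, 3.g points to other ovarian hormones or to the agonist and does not list MPA or time.

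**Working it through.** **1. The plan's own power figure.** Inputs from 3.c: n = 17, alpha 0.05 (two-sided assumed), 1 SD change, power stated as above 80%. Reading 1 SD as one SD of within-woman change, the paired t test has noncentrality δ = d√n on n − 1 degrees of freedom.

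- n = 17: δ = 1 × √17 = 4.12, power 97.2%. Normal check: Φ(4.12 − 1.96) = 98.5%.
- n = 10: δ = √10 = 3.16, power 80.3%.

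The statement holds at either sample size on this reading. If 1 SD means a cross-sectional SD, then d = 1/√(2(1 − ρ)). For an assumed within-woman correlation ρ from 0 to 0.8, power runs from 78% to over 99% at n = 17 and from 51% to 99% at n = 10. Either way, power concerns detecting a change and says nothing about its cause.

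**2. What differs between the two ends of the contrast.** 3.c does not say which visits the paired test compares. I take 6 against 9 months.

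| Component | By month 6 | Month 6 to 9 | Removed by the paired test? |
|---|---|---|---|
| Estradiol patch | none | all women | no (target) |
| MPA course | none | all women | no |
| GnRHa | 6 doses | 3 more doses | no (longer exposure) |
| Test session | second | third | no |
| Elapsed time | – | 3 months | no |

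Stable differences between women cancel in the paired test; the components above do not.

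**3. How much an uncontrolled drift could matter.** The documents give no drift, so these values are assumed. Let d be a non-estradiol shift in SDs of change, with a true estradiol effect of zero. The chance of significance, in either direction, comes from the same noncentral t.

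| d | δ, n = 17 | Significant, n = 17 | δ, n = 10 | Significant, n = 10 |
|---|---|---|---|---|
| 0 | 0 | 5% | 0 | 5% |
| 0.2 | 0.82 | 12% | 0.63 | 9% |
| 0.3 | 1.24 | 21% | 0.95 | 14% |
| 0.5 | 2.06 | 49% | 1.58 | 29% |

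These apply to the paired test for FMD and carotid compliance. The fMRI data are analysed differently (mixed-effects modelling with cluster thresholds), so the table does not describe N-back activation.

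**4. MPA timing.** A start at week 6 is day 35 (beginning of the sixth week) or day 42 (six weeks completed). Twelve days later is day 47 or 54. With 9-month testing at day 84 to 91 of add-back, the gap is at least 84 − 54 = 30 days and at most 91 − 47 = 44 days. MPA covers 12/84 = 14% of an 84-day phase. That is a measure of exposure, not of bias.

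**The case against.** The strongest reply is that nothing is hidden. Limitations concedes the missing control, Drug intervention concedes the combined regimen, and Limitations also lists other hormones, hot flashes, sleep and mood as rival explanations. This stands. The fault is that four statements of the claim were not brought into line with those concessions.

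A reader might infer that the plan commits itself to reporting a significant paired test as restoration by estradiol. The documents do not support that. After the word isolate, 3.g says more cautiously that restoration would lend support to a role for estradiol and to further work, and there is no decision rule attributing an effect to it.

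A reader might also infer that MPA could create a false restoration. On the plan's own view MPA may oppose estradiol and harm cognition, so it would work against restoration, and it ends weeks before testing. Any carry-over cannot be estimated because all add-back women receive it. It therefore matters chiefly for a null or partial result. Likewise, longer GnRHa exposure would, on the plan's hypothesis, push vascular measures away from restoration.

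The progesterone claim can be read as meaning ovarian progesterone. Because GnRHa continues, that hormone should stay suppressed while estradiol is replaced. This is a genuine strength: it makes restoration harder to attribute to recovering ovarian function. It does not supply a control, and a progestogen is still given.

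Finally, drift may be small. FMD images are coded and blinded to group, and women practise the N-back until performance stabilises. Both mitigate, but neither rules out a mean shift at a third session, nor does the test-retest reliability cited in Limitations.

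**Conclusion.** The concern holds as one of identification. The plan claims that Aim 2 isolates estradiol and distinguishes it from progesterone, other ovarian hormones or GnRHa itself. An uncontrolled within-woman contrast, under estradiol plus one MPA course on continued GnRHa, cannot show this. The missing control is the main reason; MPA is secondary. The weaker conclusion, that restoration would be consistent with a role for estradiol, remains available.

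The size of any resulting error cannot be derived from the documents. The drift percentages are illustrations that rest on assumed shifts, a two-sided 0.05 test, a 6-to-9-month contrast and one of two conflicting sample sizes.

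It is tempting to treat the placebo arm's baseline-to-6-month change as a substitute control and to call any larger change estradiol-related. The design does not support that. The placebo change covers six months rather than three, first-to-second rather than second-to-third testing, and women with intact ovarian function; nor can it remove MPA.

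**What to change.** In the Specific Aims, 1.b, 2 and 3.g, replace the claims to isolate estradiol or distinguish it from progesterone, other hormones or GnRHa. Describe Aim 2 as *the within-woman change, without a concurrent control, under estradiol-based add-back (estradiol plus one short MPA course) on continued GnRHa*.

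In 3.g, state that restoration would be consistent with a role for estradiol but could not exclude time or retest effects. Add MPA and elapsed time to the explanations for partial or absent restoration.

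In 3.c, name the visits compared by the paired test, and reconcile the add-back sample size with Drug intervention (17 against 10).

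Optionally, show the placebo arm's baseline-to-6-month change as a descriptive retest reference, stating its different interval, test occasion and hormonal state. It should not serve as a rule for attributing an effect to estradiol.

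The cost is wording and a weaker stated conclusion. No visit, arm or treatment changes.

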## **Protection of Human Subjects**

The proposed study meets the definition of a clinical trial in that it is a prospective biomedical research study of human subjects that involves random assignment to pharmacologic and behavior intervention groups. However, we consider it to be clinical research on a small number of subjects, rather than a 'clinical trial' because it is designed to reveal mechanistic consequences of the loss of ovarian function. It is not a Phase III clinical trial.

### **1. Risks to Human Subjects**

#### **a. Human Subjects Involvement and Characteristics.**

We will enroll a total of 51 subjects in this study. Subjects will be healthy women 40-60 years of age who are enrolled in the Females, Aging, Metabolism and Exercise (FAME) study ([name], PI). For detailed subject characteristics, inclusion and exclusion criteria, please see the Research Strategy, section 2.c.2.

#### **b. Sources of Materials.**

The research materials that will be collected from human subjects include:

- medical records when necessary to follow up on health status
- blood and tissue samples for screening and for study-specific outcomes, as described in the research strategy
- data from all the study procedures, as described in the research strategy

The identity of subjects and the data acquired as a result of this study will be treated with professional standards of confidentiality. All HIPAA guidelines for the protection of health information will be followed. Only members of the research team will have access to protected health information (PHI) collected from the volunteers. Confidentiality of electronic data will be maintained by using only patient identification numbers for data entry. The master document linking patient names with identification numbers will be maintained in a separate password-protected file with restricted access. Paper records will be kept in individual study charts that are stored either in a locked cabinet or in a locked office. Data records will be maintained for at least 7 years after the publication of results. At that time, the data records may be destroyed by the PI by deleting them from electronic media and by shredding paper documents, but some of the data records may be retained indefinitely. All members of the research group have individual computers that are part of the institution network with institutional oversight of security. Files that contain data that could jeopardize blinding to treatment code are password-protected to restrict access. Sharing of data with investigators or monitoring personnel outside the institution is typically facilitated by electronic transfer, in a manner that is compliant with HIPAA regulations.

